13.3 Accrual and Feasibility

The study design requires a total of 120 participants for screening evaluation with approximately 110 moving forward to randomization (55 total participants per arm) due to anticipated screen failures of approximately 8% prior to randomization. We further expect up to 10% of participants to drop out or otherwise become non-evaluable by 1 year; this rate will be reflected in power calculations for parts 1 and 2. An additional 10% expected drop out or exclusion rate between 1 and 3 years is expected, reflected in the power calculations for part 3. We expect to enroll a minimum of 1 participant per month for each of the participating CPN sites, for an overall accrual rate of 8 participants per month. With this accrual rate and with a 3-6 month ramp up for participating organizations, we plan to complete accrual in about 18 months. Accounting for patient follow-up, data entry, and analysis, the part 1 portion of the study is expected to be completed in about 22 months, followed by an additional 12 months for part 2 and an additional 24 months for part 3. The entire study duration is expected to take approximately 62 months (5.1 years), if we complete all 3 parts of the study.

13.4 Primary Objective, Endpoint, Analysis Plan

The primary objective for this study is to compare the ratio of the week 12 to week 0 IgG levels between the MUC1 vaccine and placebo. It is hypothesized that this ratio will be increased in patients treated with the MUC1 vaccine as compared to patients receiving the placebo. Prior data from a pilot study of 39 patients that were treated with the MUC1 vaccine³⁷ showed a mean IgG ratio of 6.46 with a standard deviation of about 10. Assuming equal standard deviations (i.e. 10) across the MUC1 and placebo groups, and assuming up to a 10% drop-out rate by year 1 (presumably less by 12 weeks), retaining at least 50 evaluable participants per arm yields at least 86% power to detect an increase in the mean IgG ratio from 1 to 6.5 for placebo vs. MUC1 (effect size = 0.55), using a 1-sided t-test with a significance level of 0.05. If the data are not normally distributed, we will use the Wilcoxon Rank-Sum test for this primary endpoint analysis. If the vaccine shows a significant increase in the 12-week immune response rate as compared to placebo, we will proceed to Part 2.

13.5 Secondary Objectives, Endpoints, Analysis Plans

As discussed previously, there will be key powered secondary endpoints for this study across all 3 parts.

1) Immune response at 12 weeks (Part 1): The key secondary endpoint for Part 1 will compare the proportion of patients that have at least a 2-fold increase in the IgG ratio (week 12/week 0) between MUC1 and placebo. Based on the pilot study³⁷, we hypothesize that around 40% of vaccinated participants will demonstrate a 2 fold increase in MUC1 titer at week 12 compared to around 10% for the placebo arm. Assuming a drop-out rate of up to 10% by 1 year (presumably less by 12 weeks), retaining at least 50 evaluable participants per arm provides 94% power to detect an increase in the 12-week immune response rate from 10 to 40%, assuming a 2-sided significance level of 0.05 (nQuery Advisor 6.01).

2) Booster Response at 1 year (Part 2): The key secondary endpoint for Part 2 will assess the booster response at week 55 vs. week 52 for the vaccine as compared to placebo. Based on the pilot study, we expect 75% of week-12 responders will respond with a doubling of MUC1 antibody levels, or about 35% of the overall sample. We expect the 1-year response rate to be around 10% in the placebo group. Of the 110 randomized participants (55/arm), we expect that up to 10% will drop out by 1 year, leaving

approximately 100 participants evaluable for this analysis (50/arm). With 50 evaluable participants per arm, we would have 92% power to detect an increase in the 1-year immune response rate from 10 to 35%, assuming a 1-sided significance level of 0.05 (nQuery Advisor 6.01). We will also compare the actual IgG ratio values between the 2 treatment arms as well. If the booster vaccine shows a significant increase in the 1-year immune response as compared to placebo and a response rate that exceeds 15%, we can proceed to Part III.

3) Adenoma recurrence rate at 3 years (Part 3): Part 3 will evaluate the adenoma recurrence rate at least one year and up to 3 years. The adenoma recurrence rate at 3 years in participants with an adenoma is generally around 40-50%³³. Assuming an additional 10% drop out rate between years 1 and 3, we will have 90 participants (45/arm) evaluable for this endpoint, which will provide >80% power for the different effect sizes shown in the table below (1-sided alpha = 0.05).

# Evaluable	Effect Size (delta)	Power	1-sided alpha
90 (45/arm)	50 vs. 25%	79%	0.05
90 (45/arm)	45 vs. 20%	82%	0.05
90 (45/arm)	40 vs. 15%	85%	0.05

4) As an exploratory analysis, we will also evaluate the adenoma recurrence rate from surveillance exams occurring at least 1 year and up to 3 years after Week 0 vaccine administration between MUC1 and placebo by excluding adenomas ≤ 5 mm, adenomatous tissue that may represent residual adenoma at the site of a previous adenoma, and adenomatous tissue detected in the same segment of the bowel as the previous advanced adenoma. These adenomas are excluded since they may represent missed or residual adenomas from the baseline exam. These analyses are exploratory.

5) Participant-reported injection site reaction information will be collected by use of a participant-completed Vaccine Report Card (Appendix E). Descriptive statistics will be used to summarize these data and compare the data between study arms.

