2.3 Rationale

Completed Feasibility study of MUC1 Vaccine at U. of Pittsburgh

We enrolled 40 participants who received MUC1/Poly ICLC vaccine at 0, 2, and 10 weeks and antibody titers were evaluated prior to each vaccination and at week 12, 28 and 52³⁴. In the 39 participants that received all three initial doses of vaccine, 17 (44%) had over a two-fold ratio increase at week 12, ten participants had ratios over 4.5 fold, and another 4 participants had a ratio increase from 1.4 – 2.0. The kinetics of the response were similar, with peak antibody levels generally occurring after the third injection. As expected, circulating antibody levels tended to decline over the next year with clearance of the vaccine antigen.

Response to Booster vaccine

To test for the presence of a vaccine-induced T cell memory response, participants received a booster dose of vaccine at 1 year. Of the 16 participants who responded to the initial vaccination and received the booster, 12 (75%) had a two-fold ratio increase when comparing week 54 to week 52. Three of the 4 who didn't have a two-fold elevation at week 54 had maintained high levels of antibody at week 52, hence did not manifest a 2 fold ratio increase at week 54. Overall, the results suggest that responders established a T cell memory response to the MUC1 antigen.

Adverse Events

Over 150 vaccinations were administered in the pilot study. No adverse events above grade 1 were identified, and no unanticipated adverse events were observed. Most participants developed erythema with soreness at the injection site. Some developed short lived fever and muscle aches, which respond well to analgesics such as Tylenol. We had nearly 100% compliance with the study protocol. Participants were monitored with immunofluorescent ANA titers pre vaccination and at 1 year. No participants have developed a change in ANA titer and no new autoimmune diseases were observed.

Figure 2:

[figure not shown]

Figure 2A: Ratio response in MUC1 antibody.
Figure 2B: Kinetics of response to vaccination at 0, 2, and 10 weeks (arrows under x axis) and to booster vaccine at week 52.

Evaluation of Immune Non-Responders

Lack of response to vaccination was correlated with high levels of circulating myeloid-derived suppressor cells but not to circulating T regulatory cells.

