5.7 Adherence/Compliance

5.7.1 All vaccine/placebo will be administered by appropriately trained study personnel at each site. Vaccine/placebo administration will be documented on the Intervention Administration CRF.

5.7.2 Individuals who receive the Week 0, Week 2, and Week 10 injections will be considered evaluable for the primary endpoint. Individuals who receive the Week 53 injection will be considered evaluable for the Part II key secondary endpoint. Individuals from whom data and specimens are collected for a subsequent clinical colonoscopy occurring at least 1 year (52 weeks) after the Week 0 injection will be considered evaluable for the Part III key secondary endpoint.

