13.9 Interim Analyses

Part I: The Part 1 primary endpoint analysis will be the first interim analysis. If the MUC1 vaccine is shown to significantly increase the IgG ratio as compared to placebo, we will move into the Part 2 portion of the study. This is defined in detail in Section 13.4.

Part II: If the booster vaccine shows a significant increase in the 1-year immune response as compared to placebo and the response rate exceeds 15%, we can proceed to Part III.

Study enrollment and implementation will not be halted for these analyses unless the results indicate that the study should not proceed to the next Part.

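### Section 13.5: the 35% booster rate behind the Part 2 power does not follow from its stated derivation (30–33%), and the Part 3 claim of more than 80% power covers a row printed as 79%

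*Combined protocol and SAP*

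**What the plan says.** All of these places are in the combined protocol and SAP.

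- **Section 13.5, item 2 (Part 2):** "we expect 75% of week-12 responders will respond with a doubling of MUC1 antibody levels, or about 35% of the overall sample". For the control arm: "We expect the 1-year response rate to be around 10% in the placebo group". With 50 evaluable per arm and a one-sided 0.05 level, the plan states 92% power for 10% versus 35%.
- **Section 13.5, item 1 (Part 1):** the week-12 planning rate is "around 40% of vaccinated participants will demonstrate a 2 fold increase in MUC1 titer at week 12".
- **Section 2.3, pilot study:** of 39 participants given all three doses, "17 (44%) had over a two-fold ratio increase at week 12". For the booster: "Of the 16 participants who responded to the initial vaccination and received the booster, 12 (75%) had a two-fold ratio increase". No booster result is given for pilot non-responders.
- **Section 5.7.2:** "Individuals who receive the Week 53 injection will be considered evaluable for the Part II key secondary endpoint". Week-12 response is not a condition.
- **Sections 13.5 item 2 and 13.9:** moving to Part III depends on a significant Part 2 difference and a response rate above 15%.
- **Section 13.5, item 3 (Part 3):** 45 per arm, "which will provide >80% power for the different effect sizes shown in the table below". The table prints 79% for 50 versus 25%, 82% for 45 versus 20%, and 85% for 40 versus 15%.

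**The concern.** The Part 2 sentence offers 35% of the whole arm as another way of stating 75% of week-12 responders. That is a simple product, and it does not come to 35% with either week-12 rate in the documents. The 35% is the only vaccine-arm input to the 92% power.

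A significant Part 2 result is one of the conditions for proceeding to Part III, which carries the adenoma recurrence endpoint. The 92% therefore tells readers how likely the trial is to clear that condition if the vaccine works as expected. If the input is really 30%, the chance of missing significance is about 19% rather than 8%.

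The Part 3 sentence is a separate and smaller matter: the text and the table directly below it disagree about one of three scenarios.

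**Working it through.** **Method.** Pooled-variance normal approximation for two proportions, n per arm, one-sided 0.05 (z = 1.645):

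power = Φ{ (|p1 − p2| − 1.645 × s0) / s1 }, with s0 = √[2·p̄(1 − p̄)/n], s1 = √[(p1(1 − p1) + p2(1 − p2))/n], p̄ = (p1 + p2)/2.

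**Step 1. Reproduce the plan's Part 2 figure.** n = 50, p1 = 0.35, p2 = 0.10. Then s0 = 0.0835, s1 = 0.0797, and (0.25 − 1.645 × 0.0835)/0.0797 = 1.413. Φ(1.413) = 92.1%, against 92% stated. The power calculation is sound once 35% is accepted.

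**Step 2. Check the 35%.**

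- Plan's week-12 rate: 0.75 × 0.40 = 30.0%.
- Pilot's week-12 rate: 0.75 × 17/39 = 32.7% (33.0% using the rounded 44%).
- Week-12 rate needed to reach 35% from responders alone: 0.35/0.75 = 46.7%, which is above both figures.

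**Step 3. Allow for non-responders.** Everyone boosted counts, so the arm rate is 0.75r + q(1 − r), where r is the week-12 response rate and q the doubling rate in boosted week-12 non-responders. The plan gives no q. Solving for 35%:

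- r = 0.40: q = (0.35 − 0.30)/0.60 = 8.3%.
- r = 17/39: q = (0.35 − 0.327)/0.564 = 4.1%.

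These values are solved backwards from 35% and are not evidence for it. As an illustration, suppose the plan's 10% placebo rate also applied to vaccine-arm non-responders:

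- r = 0.40: 0.30 + 0.60 × 0.10 = 36.0%.
- r = 17/39: 0.327 + 0.564 × 0.10 = 38.3%.

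**Step 4. Power at each rate (50 per arm, placebo 10%, one-sided 0.05).**

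| Vaccine-arm rate | Basis | Normal approximation | Fisher exact |
|---|---|---|---|
| 30.0% | 75% of 40%, responders only | 81.1% | 74.8% |
| 32.7% | 75% of 17/39, responders only | 87.9% | 83.2% |
| 35.0% | as stated | 92.1% | 88.7% |
| 36.0% | 40% base, non-responders at 10% | 93.6% | 90.6% |
| 38.3% | 17/39 base, non-responders at 10% | 96.1% | 94.1% |

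By the normal approximation the chance of missing significance is 12–19% for responders only, 8% at 35%, and 4–6% with non-responders at 10%. Section 13.5 does not name the Part 2 test, so both columns are shown.

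**Step 5. Part 3, 45 per arm, same formula.**

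- 50 versus 25%: (0.25 − 1.645 × 0.1021)/0.0986 = 0.833, giving 79.8% (printed 79%).
- 45 versus 20%: 82.1% (printed 82%).
- 40 versus 15%: 85.4% (printed 85%).

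The table reproduces to within a point, and its first row is below 80% both as printed and as recomputed.

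**The case against.** **Much of the Part 2 gap may be rounding.** The sentence rests on the pilot, whose 44% gives 33%, and the plan says only that the figure is approximate. Item 1's 40% is itself a rounded-down version of the pilot rate. From the pilot base the power loss is about four points (88% against 92%). This is fair as far as it goes, but 35% is not a rounding of the 30% that item 1 implies.

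**The endpoint is not restricted to responders.** Under section 5.7.2 the responders-only product is the arm rate only if no boosted non-responder doubles. Applying the plan's own 10% placebo rate to them gives 36–38%, so 35% could even be slightly conservative. This stands, and it limits the point: what is shown is a missing step in the derivation, not a wrong arm rate. A reader might infer that the true rate is 30–33% and Part 2 is underpowered. The documents do not support that, because they contain no data on boosted non-responders in either direction. Nor do they support saying that the 92% is miscalculated; it reproduces from its stated inputs.

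**No decision turns on it.** The Part III condition is applied to observed data, not to the planning rate. That is also correct. The reassurance that power stays above 80% throughout, however, holds only for the normal approximation; a one-sided Fisher test gives 75% at 30%.

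**The Part 3 slip is disclosed.** The 79% sits directly below the sentence, and other methods put that row slightly over 80% (unpooled 81.3%, exact power of the z test 80.5%). The plan nevertheless prints 79%, so its sentence contradicts its own table.

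**Conclusion.** The point holds as a minor correction to stated planning figures.

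In Part 2, the stated derivation gives 30% (plan's week-12 rate) to 33% (pilot rate), not 35%. The corresponding power is 81–88% by the formula that reproduces the plan's 92%, or 75–83% by one-sided Fisher exact (89% at 35%). The 35% requires an unstated contribution from boosted week-12 non-responders, and whether the true arm rate lies above or below 35% cannot be settled from the documents.

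In Part 3, the claim of more than 80% power is contradicted by the 79% row; the other two rows are consistent with it.

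These results rest on 50 and 45 evaluable per arm, a 10% placebo booster rate, the 75% taken from 12 of 16 pilot responders, and a one-sided 0.05 level, all as the plan states. The 10% for vaccine-arm non-responders is an illustrative assumption only. Nothing here calls for a change to the sample size or to the rule for proceeding to Part III.

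**What to change.** **Section 13.5, item 2.** State that 75% of week-12 responders corresponds to 30–33% of the vaccine arm, with 81–88% power by the normal approximation, and show this beside the 92% at 35%. If 35% is kept as the planning rate, give its actual source. One possible source is the plan's 10% placebo doubling rate applied to boosted non-responders, which gives 36–38%. A 4–8% non-responder rate should not be inserted simply because it makes the sum come to 35%; no pilot data support it. Name the test to which the power refers, since the normal approximation and Fisher exact differ by about six points at 30%.

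**Section 13.5, item 3.** Replace the claim of more than 80% power with 79–85% power, matching the table.

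**Cost.** Text changes only, with no added participants, visits or time. The one downside is a less favourable stated power for Part 2.

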13. STATISTICAL CONSIDERATIONS

13.1 Study Design/Description

This is a randomized Phase II double blind placebo controlled trial designed to assess the effects of the MUC1-1 peptide with poly-ILC adjuvant vs. placebo. There will be 3 "Parts" to the study to allow periodic monitoring and the opportunity to evaluate whether to proceed after each part. The key endpoints from each part are listed below:

Part I: The ratio of the week 12 to week 0 IgG levels will be calculated and compared between the MUC1 vaccine and placebo (primary endpoint, see 13.4).

Part II: Assessment of the booster response at week 55 vs. week 52 (T55/T52) for the vaccine as compared to placebo (key secondary endpoint, see 13.5)

Part III: Comparison of the adenoma recurrence rate from surveillance exams occurring at least one year and up to three years after Week 0 vaccine administration – MUC1 peptide versus placebo. All patients will be followed for this endpoint (key secondary endpoint, see 13.5)

In addition to these key powered endpoints for the 3 different parts, we will also assess the following additional secondary endpoints:

- Comparison of adverse events between the MUC1 vaccine and placebo during part 1 and 2 (13.7).
- To assess patient –reported vaccine-related side effects from the Vaccine Report Card.
- Comparison of the proportion of patients with at least a 2-fold increase in the IgG ratio between the 2 arms at 12 weeks (13.5).
- Comparison of the adenoma recurrence rates between MUC1 and placebo by excluding the following types of adenomas. These adenomas are excluded since they may represent missed or residual adenomas from the baseline exam. These analyses are exploratory.
 - Participants with adenomas ≤ 5 mm,
 - Participants with adenomatous tissue which may represent residual adenoma at the site of the previous advanced adenoma,
 - Participants with adenomatous tissue detected in the same segment of the bowel as the previous advanced adenoma.
- Assessment of participant-reported injection site reaction events from the Vaccine Report Card (Appendix E).

In addition, we will assess the following translational endpoints (see 13.10):

- To compare the anti-MUC1 antibody titer at the time of surveillance colonoscopy for the purpose of evaluating the anti-MUC1 antibody response in relation to adenoma recurrence. Since surveillance colonoscopy is generally at 3 years after an advanced adenoma, this titer will typically be obtained at approximately week 156.

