13.2 Randomization/Stratification

Participants will be randomized in a 1:1 fashion to one of two arms (MUC1 vs. placebo), using a dynamic allocation procedure called the Pocock-Simon⁴², which balances the marginal distributions of the stratifications factors across the intervention groups and has been shown to be able to accommodate a large number of factors (10-20) without difficulty⁴³. For this study we will use the following stratification factors: number of adenomous polyps removed ≥ 3 vs. < 3 and gender.

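### The Part III recurrence powers (79/82/85%) assume Part III is run; if the two preceding significance gates bind, the chance of reaching it and detecting the effect is about 63–74% under independence

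*Combined protocol and SAP*

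**What the plan says.** Section 13.5 item 3 states that "we will have 90 participants (45/arm) evaluable for this endpoint, which will provide >80% power" at one-sided 0.05. Its table gives 79% (50 vs 25%), 82% (45 vs 20%) and 85% (40 vs 15%). The only loss it allows for is attrition: "Assuming an additional 10% drop out rate between years 1 and 3".

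The path to Part III is set out elsewhere:

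- **Part I gate.** Section 13.4 ties progression to a significant increase in the 12-week immune response rate, after which "we will proceed to Part 2". Section 13.9 ties the same step to a significant increase in the IgG ratio and refers back to 13.4 for the detail.
- **Part II gate.** Sections 13.5 item 2 and 13.9 require a significant booster result "and the response rate exceeds 15%, we can proceed to Part III".
- **Stopping.** Section 13.9 lists both under interim analyses and says the study is not halted for them "unless the results indicate that the study should not proceed to the next Part".
- **Against strict gating.** Section 13.1 presents the Parts as a chance to decide whether to continue, and says of recurrence: "All patients will be followed for this endpoint".

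**The concern.** Recurrence is the trial's only clinical endpoint. A sponsor or monitoring board reading 13.5 could take the above-80% statement as the chance that this trial, run as planned, detects the assumed recurrence effect. It is that chance only if Part III is always reached. Under the gated reading, a vaccine that meets every design assumption can still be stopped by a chance non-significant result in Part I or Part II. The plan nowhere states how often that would happen. Those who apply the gates should have that figure in front of them.

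**Working it through.** **Inputs, all from Section 13**

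- Part I gate as mean IgG ratio: 86% power (difference 5.5, SD 10, 50/arm, one-sided 0.05; 13.4).
- Part I gate as 2-fold response rate: 94% (40 vs 10%, 50/arm, two-sided 0.05; 13.5 item 1).
- Part II gate, booster response: 92% (35 vs 10%, 50/arm, one-sided 0.05; 13.5 item 2).
- Part III: 79/82/85% (45/arm, one-sided 0.05; 13.5 item 3).

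**Step 1: reproduce the plan's figures.** For two proportions, with p̄ the mean of p1 and p2 and no continuity correction,

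power = Φ{ [|p1 − p2| − z·√(2p̄(1−p̄)/n)] / √[(p1(1−p1) + p2(1−p2))/n] }.

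First Part III row: p̄ = 0.375, n = 45, z = 1.645. The numerator is 0.25 − 1.645 × 0.1021 = 0.0821 and the denominator is 0.0986. The ratio is 0.833, so power is 79.8%. The other rows give 82.1% and 85.4%. The Part II gate gives 92.1%, the response-rate version of the Part I gate gives 94.6%, and the t-test version gives 86.1%. All the printed powers reproduce as stand-alone tests.

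**Step 2: the 15% condition.** With a true booster response of 35% and 50 participants, the chance of 8 or more responders is 99.9%. This condition costs almost nothing; the loss comes from the two significance requirements.

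**Step 3: probability of passing both gates, if they bind and are independent**

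- IgG-ratio gate: 0.86 × 0.92 = 0.791.
- Response-rate gate: 0.94 × 0.92 = 0.865.

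**Step 4: probability of reaching Part III and detecting the effect.** Multiply the probability of passing both gates by the reproduced Part III power (0.798, 0.821, 0.854), taking recurrence as independent of the gates. With perfectly dependent gates, the joint pass probability is the smaller of the two gate powers.

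| Part I gate | Dependence of gates | Pass both | 50 vs 25% | 45 vs 20% | 40 vs 15% |
|---|---|---|---|---|---|
| IgG ratio | independent | 0.791 | 63.1% | 65.0% | 67.6% |
| Response rate | independent | 0.865 | 69.0% | 71.0% | 73.8% |
| IgG ratio | perfect | 0.86 | 68.6% | 70.6% | 73.4% |
| Response rate | perfect | 0.92 | 73.4% | 75.6% | 78.6% |

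Using the rounded printed powers 79/82/85% instead gives 62.5/64.9/67.3% and 68.3/70.9/73.5% for the two independent rows.

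**Step 5: sensitivity to assumptions the documents do not give**

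- Correlation of 0.3–0.8 between the gates only (assumed, on a normal scale): 63–71% (IgG-ratio gate) or 69–76% (response-rate gate).
- Adding an assumed correlation of 0.2–0.4 between the gates and recurrence: 65–74% or 70–78%.
- Bounds with no assumption on dependence: 57% (0.86 + 0.92 + 0.79 − 2) to 85%.
- Booster rate: 75% of the hypothesised 40% week-12 responders is 30%, not the 35% used in 13.5. At 30%, the power of the Part II gate is about 81%, and the independence products fall to about 55–59% (IgG-ratio gate) or 60–65% (response-rate gate).

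**The case against.** **The printed figures are right.** They reproduce, they are attached to an evaluable count of 45 per arm, and the plan gives power Part by Part without calling any figure an overall chance of success. This stands. A reader might infer that the table is miscalculated, or that the power of the recurrence test is really 65–70%. The documents support neither. Once Part III is run with 45 per arm, the test has the stated power.

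**The gates may not bind.** Section 13.1 has everyone followed for recurrence, and the step to Part III is worded as permission. Timing also blurs the Part I gate: Part I is expected to finish at about 22 months, after accrual ends at about 18 months, when the earliest participants are already past week 53. If recurrence is analysed whatever the gates show, no power is lost. This stands as an unresolved question. It does not show that the gates are advisory, because 13.4, 13.5 and 13.9 make progression depend on significance.

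**No single lower figure is fixed.** The Part I gate has two definitions, and the dependence is not given. The 86% is also a floor: 55 per arm gives 88.9%, and an assumed placebo SD of 1–5 instead of 10 gives 96–99%. This stands against quoting one number. It does not rescue the above-80% claim. Even if the Part I gate were certain to be passed, the Part II gate alone leaves 0.92 × 0.854 = 78.6% in the best row when recurrence is independent of the gates.

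**Early stopping is deliberate.** An occasional false stop is the price of a staged design. This too stands, and it is why the remedy is disclosure, not redesign.

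**Conclusion.** The Part III powers are correct as conditional powers, but they are not labelled as such. If the gates bind, the chance of reaching Part III and detecting the assumed effect is about 63–68% (Part I gate as IgG ratio) or 69–74% (Part I gate as response rate) under independence. With perfectly dependent gates and recurrence independent of them, it is at most about 69–79%. Values above 80% occur only within the assumption-free bounds and would need strong dependence between recurrence and the gates, for which the documents give no value.

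A reader might also infer that a working vaccine is stopped one time in five. That holds only for the IgG-ratio gate under independence (1 − 0.791 = 21%); for the response-rate gate it is about 14%.

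Separately, the above-80% statement fails against the table's own first row, 79%, whatever the status of the gates.

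**What to change.** In Section 13.5 item 3:

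- Drop the above-80% statement.
- Label 79/82/85% as conditional on passing both gates with 45 per arm evaluable.
- Add the unconditional range beside it, stating the definition of the Part I gate, the dependence assumed and the booster rate used.

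Reconcile 13.1 with 13.4, 13.5 and 13.9 on whether the gates are binding, and reconcile 13.4 with 13.9 on whether the Part I gate tests the response rate or the IgG ratio.

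If the sponsor declares the gates advisory and recurrence is analysed regardless, the conditional figures stand and the text need only say 79–85%. That choice is a trade-off for the sponsor: where a gate fails, it means carrying on with the remaining Part III calls, records collection and one blood draw.

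The restatement itself costs wording only, with a less favourable headline figure. Neither route needs extra participants.
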